**OBJECTIVES:**

*(Describe the purpose, specific aims, or objectives. State the hypotheses to be tested.)*

Chronic back pain (CBP) can last from months to a lifetime, severely impacting patients' quality of life. Based on our human brain imaging studies and preclinical findings, the hippocampus and its network are associated with pain and pain experience in patients with chronic pain. In this study we aim to test whether a non-invasive enhancement of dorsal hippocampus activity leads to networks alteration that can modulate pain in CBP patients.

**Aim 1:** To investigate whether a novel target, dorsal hippocampus, indirectly stimulated using high frequency rTMS, will lead to an increase in hippocampal network connectivity that can modulate pain, as compared a sham control rTMS, in CBP patients.

We hypothesize that changes in pain from baseline to post-stimulation will be superior for hippocampal-target than for control stimulation (sham). Pain is primarily assessed by daily ratings on our phone app; additional questionnaires will be used as secondary exploratory outcomes.

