In this pilot study, we aim to indirectly stimulate the dorsal hippocampus to increase hippocampal connectivity and modulate pain. We will use rTMS to stimulate an area of the parietal cortex with high functional connectivity to the hippocampus, using seed-based connectivity analysis of rsfMRI data, in order to modulate hippocampal-mediated networks. It is notable that targeting hippocampal excitability using rTMS is an approach that we have pioneered. The hippocampus is not directly accessible to rTMS. We use cortical “access windows”, which are stimulation-accessible areas of the cortex that have high connectivity with the hippocampus and therefore stimulation applied to these areas can indirectly influence the hippocampus. In several experiments. We have shown that this method increases excitability and rsfMRI connectivity of dorsal hippocampus, leading to long-lasting improvements in hippocampal-dependent function. We hypothesize that dorsal hippocampal stimulation will lead to analgesic effects in CBP.

In line with the promising preclinical results we report, in this study we will collect preliminary data to systematically test whether the modulation of hippocampal network changes the experience of pain in CBP patients.

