## **POTENTIAL BENEFITS TO PARTICIPANTS**

We cannot promise any benefits; however, possible benefits include a decrease in pain as a result of the stimulation sessions. We are not able to estimate at this time the probability, magnitude or duration of benefit. We hope to define these parameters with the results of this study.

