### **Data Analysis Plan**

MRI data will be analyzed using the FSL software library [30]. Briefly, structural data will be skull-stripped and normalized to MNI space through nonlinear transformation. Functional data will be motion corrected and smoothed with a 4 mm smoothing kernel. Data will be further denoised by performing motion-censoring and regressing out the motion parameters. Finally, data will be band-pass filtered (0.01 to 0.1 Hz). Functional connectivity analyses will be carried on by performing Pearson correlations between the BOLD time series of a hippocampal seed and all other voxels in the brain. The maximal statistically significant cluster near a predetermined coordinate in the parietal cortex (see Wang et al. 2014) will be extracted, spatially warped to the subject native space, and fed into the TMS neuronavigation system for stimulation.

Statistical analyses will be performed using the software R. We use repeated-measures within-subject analysis of variance for dependent variables 1) change in painApp immediately after rTMS relative to baseline, and 2) for change in painApp in the long term (average over the second week after rTMS) relative to baseline, with independent factors being hippocampus-rTMS and sham-rTMS; with Bonferroni post-hoc comparisons. If the ANOVAs are significant and post-hoc comparisons indicate superiority of hippocampus-rTMS, we declare that the approach is a clinically important means of pain control in CBP, and newer larger studies should be launched.

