### **Power Calculation**

This study aims to collect preliminary data in humans to test whether a manipulation of the hippocampal network can lead to changes in pain experience in CBP participants. With this in mind, we will aim for a final sample size of 12 subjects. Due to possible dropouts over the course of the study, we will recruit a total of 16 subjects. If this study shows indication that the hippocampal stimulation leads to higher connectivity increase across series of hippocampal networks that modulates pain, the results of this study will be used to perform a power calculation in order to perform a future study aiming to treat chronic back pain.

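### The pain decision rule declares clinical importance from significance and direction alone, with no effect-size criterion, in a preliminary study aiming for 12 subjects

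*Combined protocol and SAP*

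**What the plan says.** The Data Analysis Plan names two dependent variables, both changes in painApp rating from baseline: immediately after rTMS, and averaged over the second week after it. Each is analysed by a repeated-measures ANOVA comparing active with sham, followed by Bonferroni post-hoc comparisons. The condition for success is "If the ANOVAs are significant and post-hoc comparisons indicate superiority of hippocampus-rTMS". The conclusion attached to it is "we declare that the approach is a clinically important means of pain control in CBP, and newer larger studies should be launched".

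Other sections describe a more modest undertaking. The Power Calculation section says "This study aims to collect preliminary data in humans" and "we will aim for a final sample size of 12 subjects", recruiting 16 to allow for dropout; it gives no effect size, SD, alpha or power. The Background calls the study a pilot and says "in this study we will collect preliminary data". Study Endpoints makes connectivity the main aim and pain ratings the secondary outcome. Potential Benefits to Participants says "We are not able to estimate at this time the probability, magnitude or duration of benefit", and then "We hope to define these parameters with the results of this study".

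**The concern.** The rule asks whether the difference is distinguishable from zero and which way it points. It then states a conclusion about size that neither condition examines. The plan says elsewhere that the magnitude of benefit is unknown and is to be learned from this study, yet the rule never looks at magnitude.

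Followed as written, the trial could announce a clinically important treatment when the confidence interval for each pain outcome begins at about zero. Such data are compatible with a negligible effect. The observed difference that earns the label is set by the variability of the ratings and the number of completers, so more completers lower the bar for what counts as important.

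Using pain for the rule is not the problem: the Objectives section states superiority over sham on pain as the hypothesis.

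**Working it through.** **Inputs from the documents.** Two within-subject conditions, active and sham, in a crossover; 12 subjects intended for analysis, 16 recruited; pain on a 0-10 NRS; two painApp outcomes.

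**Assumptions, because the documents are silent.** Two-sided alpha of 0.05 for each outcome; SD of the within-subject active-minus-sham difference of 1, 1.5 or 2 NRS points; both ANOVAs required, which is the natural reading of the plural; correlation between the two outcomes of 0, 0.5 or 0.9.

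**The plan's own figure.** The target of 12 cannot be reproduced, since no inputs are given. Going from 12 to 16 implies dropout of 1 − 12/16 = 25%, a rate the plan does not state.

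**Smallest observed difference that meets the rule.** With two conditions the ANOVA is a paired t test (F = t²), so the smallest significant mean difference is t(1 − α/2, n − 1)/√n × SD.

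| Case | Multiple of SD | SD 1 | SD 1.5 | SD 2 |
|---|---|---|---|---|
| n = 12, α = 0.05 | 2.201/√12 = 0.635 | 0.64 | 0.95 | 1.27 |
| n = 16, α = 0.05 | 0.533 | 0.53 | 0.80 | 1.07 |
| n = 12, α = 0.025 | 0.749 | 0.75 | 1.12 | 1.50 |

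The last row applies if Bonferroni is meant across the two outcomes, which the text does not say. At α = 0.05, a result exactly on the boundary has a 95% confidence interval from 0 to twice the estimate.

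**How often the label is given when the true difference is 0.5 point on each outcome.** Pairs of paired t tests were simulated with n = 12 and 400,000 replicates per cell, counting only results that favour active on both outcomes. Ranges run over outcome correlations 0 to 0.9. The 1-point threshold is illustrative and does not come from the documents.

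| SD | Significant on both | Also an observed mean of at least 1 point on both |
|---|---|---|
| 1 | 12%-28% | 0.2%-2.6% |
| 1.5 | 3.4%-13% | 1.1%-7.3% |
| 2 | 1.5%-8.2% | 1.2%-7.3% |

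At SD 1, about 90% to 99% of the declarations would therefore rest on an observed difference below 1 point on at least one outcome. At SD 1.5 the share is about 44% to 67%. At SD 2 it is roughly 11% to 20% (1 − 0.073/0.082 and 1 − 0.012/0.015).

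**No true difference.** Both outcomes are significant in favour of active in 0.06% to 1.4% of trials, so requiring both does not inflate error.

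**The case against.** The strongest reply is that little harm follows. The same sentence leads only to larger studies, the Power Calculation section uses the results to size a future trial, and no treatment decision hangs on the label. Pain is also the secondary outcome. With 12 subjects, significance already needs a sizeable observed effect if ratings are variable: at SD 2 it takes 1.27 points, and adding a 1-point threshold then changes almost nothing. No document says that 0.5 point is negligible. Every simulated percentage depends on requiring both outcomes and on an alpha that the plan does not state.

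Much of this stands as a limit on the size of the problem. The numerical gap is large only when the SD is near 1, and no SD is documented. The point is mainly about what may be concluded.

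It does not remove the defect. The call for larger studies is added to the declaration and does not qualify it. The secondary rank of pain makes the label harder to justify. The plan cannot rely on a large SD that it never states, and even then the interval at the boundary starts at zero. Being strict about zero is not evidence of size.

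**Conclusion.** The concern holds. The pre-specified conclusion is one that the test cannot support, and this is an error in the rule as written, not just a missing detail. The fault lies in the clinical-importance label; under the both-outcomes reading, false positives are not inflated.

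On the stated assumptions, the label can be earned by an observed difference as small as 0.64 point with 12 completers, or 0.53 point with 16, both at SD 1. How often a small true effect would receive it depends heavily on the unknown SD. The logical gap between significance and importance does not depend on the SD, on alpha, or on whether one or both outcomes are required. The estimates themselves remain valid, so this should be fixed but does not undermine the design.

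**What to change.** Replace the declaration in the Data Analysis Plan with wording such as: *A significant difference favouring hippocampus-rTMS on both painApp outcomes (two-sided 0.05 each) supports launching a larger study. Each mean difference will be reported with its 95% confidence interval, and no claim of clinical importance will be made from significance alone.* Requiring both outcomes and using 0.05 for each are choices the investigators need to confirm. They should also say whether Bonferroni applies across the two outcomes, since with two conditions it adjusts nothing within one ANOVA. A cross-reference to the future-study trigger in the Power Calculation section would help; the two overlap but do not conflict.

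If an importance claim is kept, tie it to an NRS threshold fixed before outcome data are analysed, with its source stated. Reference 28, cited for the NRS, could be examined. Its title concerns changes in pain intensity, so using it for a mean active-sham difference would need justifying.

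The wording change needs no new data; its cost is a more modest claim from a positive result. A threshold also costs power. With n = 12, SD 1.5, both outcomes and a 1-point threshold (all assumed):

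| True difference | Significance alone | Plus observed mean of at least 1 | Lower 95% limit above 1 |
|---|---|---|---|
| 1 | 31%-48% | 21%-38% | – |
| 1.5 | 78%-85% | 71%-80% | 3.4%-13% |
| 2 | 97%-98% | 97%-98% | 31%-48% |

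The observed-mean rule is cheaper, but it is weaker evidence that the true difference exceeds the threshold.

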### **Power Calculation**

This study aims to collect preliminary data in humans to test whether a manipulation of the hippocampal network can lead to changes in pain experience in CBP participants. With this in mind, we will aim for a final sample size of 12 subjects. Due to possible dropouts over the course of the study, we will recruit a total of 16 subjects. If this study shows indication that the hippocampal stimulation leads to higher connectivity increase across series of hippocampal networks that modulates pain, the results of this study will be used to perform a power calculation in order to perform a future study aiming to treat chronic back pain.

### **PROVISIONS TO MONITOR THE DATA TO ENSURE THE SAFETY OF PARTICIPANTS**

The primary protection will be careful recruitment, thereby limiting enrollment only to eligible subjects, i.e., subjects meeting all inclusion and exclusion criteria.

### **MR Imaging**

Individuals who cannot tolerate the confinement of an MRI scanner and those who may not be able to be scanned because of implanted metal devices will be excluded. Claustrophobia is the main limiting factor; we attempt to identify people at risk by having people lie in the simulation scanner (a fake scanner made to look and feel like the real one) to assess their comfort levels. There is a standard checklist of additional exclusionary items for MR scanning (e.g., implanted devices, exposure to metallic fragments at work, etc) that will be utilized prior to entering participants into the study and again prior to each imaging session. Personnel continuously query the subject in the scanner as to their overall well-being during scans and will discontinue the scan

STU#:

and relieve the subject from the discomfort at any time requested. It is possible that the anatomical scans may uncover a brain abnormality of which the participant was not aware. In such cases, the subject is removed from the study and given appropriate medical advice ([name]); his/her scans are sent to a radiologist for an opinion and this person then consults with [name]. The likelihood of this happening is low (less than 1%). Over the last 20 years of doing brain scans in various populations (healthy and not), participants often are surprised at how anxious they feel in the scanner and simply cannot tolerate it. Otherwise, subjects are usually enthusiastic in participating in trials that may lead to new discoveries that either pertain to their conditions or help other people.

## **TMS**

Individuals who cannot tolerate TMS stimulation or those who may not receive stimulation will be excluded. To minimize risk and protect participants, a trained clinical staff will be present for all the rTMS sessions (a trained clinical staff will also be present on "sham" sessions, even though in these sessions the intensity of stimulation is adjusted to a low value that cannot influence the brain). Study staff personnel continuously query the subject regarding their overall well-being during the stimulation protocols and will discontinue and relieve the subject from the discomfort at any time requested.

## **Questionnaire Risks**

To deal with the possibility that some questions may be sensitive in nature or make people feel uncomfortable, individuals will be told that they need not complete any items of entire questionnaires if they feel that doing so will cause discomfort. Because we are measuring depression, anxiety, and other mental health constructs in these questionnaires, [name], a licensed clinical psychologist, will be available to consult about any concerns that patients have about their mental health, including referrals to appropriate providers. All such participants will be given a list of referral sources in case they wish to seek mental healthcare, and participants will be invited to contact the research team with any questions about getting connected with appropriate healthcare.

## **PROVISIONS TO PROTECT THE PRIVACY INTERESTS OF PARTICIPANTS**

Privacy and confidentiality will be maintained using allocation numbers (also called participant IDs, PIDS) throughout the study with the master study list being maintained by the PI and study coordinator with availability limited to those study personnel who have a documented need for this information. All electronic information will be pass-word protected and stored on a secure server; when necessary, it will also be encrypted for extra protection.

To deal with the possibility that some questions may be sensitive in nature or make people feel uncomfortable, individuals will be told that they need not complete any items of entire questionnaires if they feel that doing so will cause discomfort. Because we are measuring depression, anxiety, and other mental health constructs in these questionnaires, [name], a licensed clinical psychologist, will be available to consult about any concerns that patients have about their mental health, including referrals to appropriate providers. All such participants will be given a list of referral sources in case they wish to seek mental healthcare, and participants will be invited to contact the research team with any questions about getting connected with appropriate healthcare.

## **COMPENSATION FOR RESEARCH-RELATED INJURY**

STU#:

If a subject is injured as a result of this study (medications, or procedures), they should seek medical treatment through their primary care physician or treatment center of choice. They will be instructed during the consent process to promptly tell the study doctor about any illness or injury. The hospital [university, researchers] will not pay for medical care required because of a bad outcome resulting from participation in this research study.

## **ECONOMIC BURDEN TO PARTICIPANTS**

Participants will not be responsible for any study-related costs because of participation in the research.

## **CONSENT PROCESS**

Informed consent is a process that is initiated prior to the individual agreeing to participate in the study and continues throughout study participation. We will be obtaining informed consent for all subjects in this study. We do not plan to enroll non-English speaking subjects, cognitive impaired individuals, individuals under 18 years of age, and or adults who are unable to consent.

The following outlines the informed consent process:

After passing the pre-screening over the phone, the participant will be scheduled for a screening visit. If possible, a copy of the IRB-approved consent form will be emailed or mailed to the subject prior to the scheduled visit.

The consent process will take place in Abbott Hall on the 10th floor clinical research exam space in a private exam room or in the CTI in a private room. The consent form will be explained to the participant (the participant will read along with staff): each section of the form will be discussed, taking time to highlight the purpose of the study, procedures, risks, confidentiality measures taken to protect the participant, and how to revoke/withdraw consent, if desired, and to answer any questions the participant may have. If staff cannot answer the question or if the participant has concerns to discuss, the study physician or PI will be contacted to speak to the participant. Subjects will be given as much time as they need to make their decision whether or not to participate. There will be a waiting period available to the participant; they will have an opportunity to take the consent document home to discuss with family, friends, and/or their physician prior to signing the document. Once the document is signed, the subject will sign and date two copies. One copy to take home and one copy to keep with the subject's source documents. The consent process will also be documented in the subject's source documents.

All participants will be re-consented should a new ICF be approved by the IRB with updated information. In cases where participants may need to be notified of new information before an ICF is approved by the IRB, subjects will be notified by phone about updated information.

This study will follow SOP: Informed Consent Process for Research (HRP-090) as well as "SOP: Written Documentation of Consent (HRP-091)."

## **NON-ENGLISH-SPEAKING PARTICIPANTS**

STU#:

Only English-speaking participants will be enrolled.

## **PROTECTED HEALTH INFORMATION (PHI AND HIPAA)**

We are committed to respect participant privacy and to keep personal information confidential. When choosing to take part in this study, participants are giving us the permission to use their PHI that includes health information in their medical records and information that can identify them. For example, PHI may include name, address, phone number or social security number. Health information that we may collect and use for this research includes:

- Results of physical examinations
- Medical history including back pain history and family history of back pain
- Lab tests, or certain health information indicating or relating to a particular condition as well as information collected by cellphone apps
- Records about study medication or drugs
- Records about MRI scans
- Substance abuse information: current recreational drug use or history of alcohol or drug abuse

The following groups of people may give the researchers information about research participants: All current and previous health care providers, including but not limited to the NMH. Once we have the health information listed above, we may share some of this information with the following people. Please note that any research information shared with people outside of NU and its clinical partners (or affiliates) will not contain subject's name, address, telephone or social security number or any other direct personal identifier unless disclosure of the direct identifier is required by law [except that such information may be viewed by the Study sponsor and its partners or contractors at the PI's office]

- Authorized members of the NU workforce, who may need to see information, such as administrative staff members from the Office for Research, Office for Research Integrity and members of the Institutional Review Board (a committee which is responsible for the ethical oversight of the study),
- Clinical affiliates, including but not limited the NMH. Individuals' participation in this clinical trial will be tracked in an electronic database and may be seen by investigators running other trials and by other healthcare providers having access to this database.
- Other University research centers and University contractors who are also working on the study,

The informed consent document will include a HIPAA authorization as well.

The results of this study may also be used for teaching, publications, or presentation at scientific meetings. However, the individual's name and personal information will not be used.

